## 2 Abbreviations and Definitions

AE	Adverse event
AUC	Area under curve
CRF	Case report form
DBPCFC	Double blind placebo controlled food challenge
IgE	Immunoglobulin E
LOAEL	Lowest observed adverse effect level
NOAEL	No observed adverse effect level
OIT	Oral Immunotherapy
QoL	Quality of life
SAP	Statistical analysis plan
SPT	Skin prick test
SUSAR	Suspected unexpected serious adverse reaction
WAO	World Allergy Organisation

## 3 Introduction

The aim is to develop a new treatment for a common, serious and currently untreatable condition. We propose a definitive study of the efficacy of peanut oral immunotherapy (OIT) as a treatment for peanut allergy. Immunological mechanisms will be studied. We have conducted a pilot which demonstrated proof of concept; the present study includes larger numbers and a control group, with power to detect outcome at the 0.05 significance level. There will be two inter-dependent work packages. Package 1 will be a randomized comparison of intervention versus the current best management. Package 2 will confirm efficacy in the waiting list group when subsequently treated and allow an estimate of the overall success rate to within 10%.

## 4 Study Objectives and Endpoints

### 4.1 Study Objectives

The overarching objective is to determine efficacy of oral immunotherapy in peanut allergy. We will determine whether the planned intervention is successful in the intervention group compared to control (package 1), and whether it is successful when offered to the control group (package 2). Other objectives include identification of immunological changes over time, and improvement in quality of life scores.

## 4.2 Endpoints

### 4.2.1 Primary Endpoint

Incidence of desensitisation to peanut at the end of six months.

### 4.2.2 Secondary Endpoints

- Incidence of desensitisation to peanut in waiting list patients after receiving the active intervention (end of phase 2)
- Incidence of response to treatment(end of phase 1 (intervention group) and end of phase 2 (waiting list group))
- Fold and absolute increase in threshold (maximum tolerated peanut protein (mg))
- Change in quality of life (QoL) scores from baseline to the end of phase 1
- Change in QoL scores before and after immunotherapy (Baseline to phase 1(intervention group) or phase 1 to phase 2 (waiting list group).
- Change in immunological outcomes (Basophil histamine release, Peanut IgE, Total IgE, and skin prick test diameter (SPT))
- Change in severity of symptoms (World Allergy Organisation (WAO) score) from baseline to the end of phase 1

## 4.3 Derived variables

- Desensitisation to peanut – able to ingest 1400mg peanut protein without reacting
- Response to treatment – able to ingest 800mg protein without reacting, after immunotherapy

[figure not shown]

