## 5.2 Inclusion–Exclusion Criteria and General Study Population

### 5.2.1 Inclusion Criteria

1. Subjects aged between 7 and 15 years of age
2. Subjects with peanut allergy confirmed by a clinical history of a typical rapid onset immediate type hypersensitivity reaction to definite peanut ingestion.
3. Positive skin prick test to peanut (extract ALK–Abello, Hørsholm, Denmark) defined by wheal  $\geq 3$ mm in the presence of a negative control and positive histamine control.
4. Positive double blind placebo controlled food challenge performed according to international consensus guidelines
5. Informed consent obtained from parent / guardian or participant, as appropriate.

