## 5.3 Randomisation and Blinding

Subjects were allocated using minimisation to avoid imbalance of confounding factors between groups, with a random element using a weighting probability of 0.8 – i.e. patients were allocated to the group which would provide optimal balance with 80% probability.

The minimising variables were age (7–<12, 12–15), sex, allergy severity (mild, moderate, severe, never eaten), asthma, serum peanut IgE ( $\leq 28$ ku/l,  $>28$ ku/l), challenge threshold ( $>5$ mg, 50–200mg,  $>200$ mg) and other current food allergies.

Patients are not blinded to their randomised groups. However the primary outcome will be assessed using a double blind placebo controlled food challenge (DBPCFC). On the challenge neither the investigator, nurse nor the participant will know whether the participants dose is peanut or placebo.

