### 5.4 Study Variables

The visit schedule is shown below:

Week	0	Phase 1										Phase 2									
		2	4	6	8	10	12	14	16	18	24	26*	28*	30*	32*	34*	36*	38*	40*	42*	48*
Active immunotherapy visit	1	2	3	4	5	6	7	8	9	10	11	-	-	-	-	-	-	-	-	-	-
Waiting list visit*	(Baseline)	-	-	-	-	-	-	-	-	-	2	3*	4*	5*	6*	7*	8*	9*	10*	11*	12*
Demographics	x																				
Other allergies	x																				
WAO score (historical)	x																				
DBPCFC (NOAEL, LOAEL, WAO score)	x									x											x
Peanut SPT	x									x											x
Other nut SPT	x									x											x
Peanut specific IgE	x									x											x
Total IgE	x									x											x
Basophil histamine release	x									x											x
Tryptase	x																				
QoL questionnaire	x									x											x
OIT updose*		x	x	x	x	x	x	x	x	x	x	x	x	x	x	x	x	x	x	x	x

*\*Only waiting list patients who are not desensitised to peanut after 24 weeks undergo immunotherapy from week 26 to 48*

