### **9.2 Secondary Efficacy Analyses**

- The incidence of desensitisation to peanut in the waiting list group after receiving the active intervention (end of phase 2) will be reported and compared with the incidence of desensitisation to peanut in the intervention group (end of phase 1) using Fishers exact test.

- Incidence of response to treatment (i.e. desensitisation to the maintenance immunotherapy dose of 800mg) will be compared between the intervention and waiting list groups using Fishers exact test. Multiple logistic regression will be used to adjust the odds ratio of response to treatment for baseline characteristics described in section 7.2.
- The absolute and fold change in threshold will be compared within and between groups using paired and independent sample t-tests respectively. This may be extended to a linear regression adjusting for baseline covariates (section 7.2)
- QoL scores at the end of phase 1 will be compared between groups using a Mann Whitney U test.
- Change in QoL scores before and after intervention in both groups (Intervention: Phase1 – baseline; Waiting list: Phase 2– Phase 1) will be investigated within groups using a Wilcoxon sign rank test and then between groups using a Mann –Whitney U test.
- Change in peanut IgE from baseline to end of phase 1 will be compared between groups using a Mann–Whitney U test.
- Change in AUC (CD63MFI and %CD63 positive cells) of Basophil histamine release from baseline to end of phase 1 will be compared between groups using a Mann–Whitney U test
- Change in SPT results (peanut and other nuts) from baseline to end of phase 1 will be compared between groups using a Mann– Whitney U test
- Change in WAO score from baseline to end of phase 1 will be compared between groups using a Mann – Whitney U test

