Comparison of change in peanut immunological outcomes between treatment groups	2.6	Full analysis	Peanut IgE Total IgE Peanut SPT Other nut SPT Basophil histamine release CD63MFI (AUC) Basophil histamine release %CD63 positive cells (AUC)	Baseline and 6 months	Treatment	median, range, difference, 95% CI	Mann-Whitney U tests
Comparison of change in WAO score between treatment groups	2.7	Full analysis	WAO score	Baseline and 6 months	Treatment	median, range, difference, 95% CI	Mann-Whitney U tests
Predictors of treatment response	2.8	All patients who underwent immunotherapy	Response to immunotherapy	6 months (or 12 months for Waiting list group)	Treatment Age Sex Asthma Eczema Rhinitis Weight	odds ratios, 95% CI	Logistic regression

Sensitisation to tree nuts

Peanut specific IgE

Peanut SPT wheal diameter

Basophil AUC of CD63MFI against peanut protein concentration

QoL score

Family history of allergy peanut

Baseline NOAEL

Adverse events per dose	2.9	Safety population	Mouth itching Abdominal pain Nausea Vomiting Diarrhoea Urticaria Angioedema Erythema Rhinitis Wheezing Laryngeal oedema Cardiovascular collapse Fainting Admission to ITU Serious adverse reaction SUSAR	End of study	Treatment	n, %	NA
-------------------------	-----	-------------------	---	--------------	-----------	------	----

Use of nebulised beta 2 agonist

Use of intramuscular adrenaline

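### Response to treatment is judged only on tolerating 800 mg after immunotherapy, so a waiting-list child who already tolerated 800 mg but not 1400 mg at week 24 would count as a responder without any change

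*SAP*

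**What the plan says.** Section 4.3 gives two derived outcomes with different cut-offs: "Desensitisation to peanut – able to ingest 1400mg peanut protein without reacting" and "Response to treatment – able to ingest 800mg protein without reacting, after immunotherapy". Section 9.2 repeats the lower cut-off: "Incidence of response to treatment (i.e. desensitisation to the maintenance immunotherapy dose of 800mg) will be compared between the intervention and waiting list groups". Section 4.2.2 sets the time points: "Incidence of response to treatment(end of phase 1 (intervention group) and end of phase 2 (waiting list group", so each group is assessed after its own course of treatment.

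The footnote to the visit schedule in section 5.4 states the condition for phase 2: "Only waiting list patients who are not desensitised to peanut after 24 weeks undergo immunotherapy from week 26 to 48". Section 5.1 describes the same children as those still allergic at the end of phase 1.

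At entry, section 5.2.1 requires a "Positive double blind placebo controlled food challenge performed according to international consensus guidelines" and gives no upper limit on the reacting dose. The minimisation factors in section 5.3 include "challenge threshold ( $>5$ mg, 50–200mg, $>200$ mg) and other current food allergies", so the top threshold stratum has no ceiling.

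Table 2.8 (section 13.1) models response in all patients who underwent immunotherapy and lists "Baseline NOAEL" among the predictors. Section 5.4.1 defines the NOAEL as a cumulative dose, and the schedule records it at each challenge.

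**The concern.** The name of the outcome, and a table of its predictors, invite the reader to take it as an effect of treatment. As defined it is a state after treatment. A child who was already in that state when immunotherapy began counts the same as one whom treatment brought there.

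This matters for three reasons:

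- **The reported rate.** Each child who already tolerated 800 mg, and still does, adds to the numerator without having changed.
- **The group comparison.** On the time points in section 4.2.2, both groups have been treated when response is assessed. No untreated arm is present to cancel out prior tolerance. The error need not be equal either: every child reacts at the entry challenge, yet section 6 plans on 30% of untreated controls tolerating 1400 mg by six months. If thresholds do rise untreated, prior tolerance of 800 mg would be commoner at the start of phase 2 than at entry.
- **Table 2.8.** A child starting at 800 mg or more is a responder unless tolerance is lost, so starting threshold predicts response partly by construction. For the waiting list, the starting value is the week-24 NOAEL and not the baseline one that is listed.

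**Working it through.** **1. The plan's own figures (section 6).** Inputs: 64% versus 30% desensitised at 1400 mg, Fisher's exact test, two-sided 5%, 90% power. By exact enumeration, power is 89.6% with 48 per group and 90.6% with 49, so 49 is the smallest size that reaches 90%. Dropout: 49/0.95 = 51.6, rounded up to 52 per group, 104 in all. Phase 2 entrants: 0.70 × 49 = 34.3, rounded up to 35. All the stated figures reproduce. They concern the 1400 mg endpoint, so the present point leaves them as they are.

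**2. The cut-offs side by side, for a waiting-list child at week 24.**

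| Week-24 NOAEL | Desensitised (1400 mg)? | Enters phase 2? | Already meets the 800 mg cut-off? |
|---|---|---|---|
| below 800 mg | no | yes | no |
| 800 to under 1400 mg | no | yes | **yes** |
| 1400 mg or more | yes | no | yes |

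The middle row follows from the definitions alone. Whether any child can fall in it depends on whether the challenge has a cumulative step from 800 mg up to just under 1400 mg. The SAP does not give the steps.

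**3. What each such child does to the rate.** Let k be the number of the 35 entrants who already tolerate 800 mg (all assumed to keep that tolerance), and r the response rate in those starting below 800 mg. The SAP gives neither; both are assumptions.

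Counted rate = [k + r(35 − k)]/35. Newly reaching 800 mg = r(35 − k)/35.

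| k | Counted (r = 64%) | Newly reaching 800 mg (r = 64%) | Counted minus r: r = 50% | r = 64% | r = 80% |
|---|---|---|---|---|---|
| 0 | 64.0% | 64.0% | 0 | 0 | 0 |
| 2 | 66.1% | 60.3% | 2.9 points | 2.1 | 1.1 |
| 4 | 68.1% | 56.7% | 5.7 | 4.1 | 2.3 |
| 7 | 71.2% | 51.2% | 10.0 | 7.2 | 4.0 |
| 10 | 74.3% | 45.7% | 14.3 | 10.3 | 5.7 |

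Example, k = 7: (7 + 0.64 × 28)/35 = 24.92/35 = 71.2%.

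**4. A conditional size for k.** Assume week-24 thresholds are log-normal with 30% above 1400 mg, natural-log SD of 1 to 3, and challenge steps that separate 800 from 1400 mg. Then z = 0.524, ln(1400/800) = 0.560, and P(NOAEL ≥ 800) = 1 − Φ(0.524 − 0.560/SD).

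| SD | P(≥ 800 mg) | 800 to <1400 mg (minus 0.30) | Share of entrants (÷ 0.70) | Of 35 |
|---|---|---|---|---|
| 1 | 0.514 | 0.214 | 31% | 10.7 |
| 1.5 | 0.440 | 0.140 | 20% | 7.0 |
| 2 | 0.403 | 0.103 | 15% | 5.2 |
| 3 | 0.368 | 0.068 | 10% | 3.4 |

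If only 5% of untreated children exceed 1400 mg, the same model gives about 1 to 3 of 35.

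**The case against.** The strongest reply is that the SAP does not show that any such child exists. Challenge steps and top dose are details that a SAP commonly leaves to the protocol, which is not shown. If no cumulative step lies in the 800 to under 1400 mg range, the problem is empty. This stands, and it limits the point to a gap in the definition.

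The log-normal model can also be challenged. It implies untreated medians of 829 mg (SD 1) down to 290 mg (SD 3), with 92% down to 55% of untreated children above 200 mg. The minimisation cut-points of 5, 50 and 200 mg suggest that the planners expected many children lower than that. The 30% is a planning rate, not a threshold distribution. A mixture in which 30% tolerate 1400 mg and the rest react at low doses fits it equally well and leaves the range nearly empty. This stands too: a reader might take 3 to 11 of 35 as an estimate, and the SAP does not support that.

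A third reply is that response is meant as a state, tolerance of the maintenance dose, and that change is covered elsewhere, by absolute and fold change in threshold and by adjustment for baseline characteristics, which include the NOAEL. These help interpretation. They do not alter the reported incidence or its Fisher test, and a baseline covariate is not the pre-treatment value for the waiting list.

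On Table 2.8, a starting threshold that predicts outcome is also ordinary prognostic information. Because the listed covariate is the baseline value, prediction by construction through that covariate depends mainly on the entry route, which is the less certain one.

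Finally, dropping prior tolerators outright would set aside treated children, using a post-randomisation value in one arm, although section 9 calls for intention-to-treat analyses. That is a fair reason to keep the all-treated rate and add to it.

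**Conclusion.** The definition is incomplete for what it is used to show. At week 24 the gap follows from the SAP's own cut-offs: 1400 mg decides entry to phase 2 and 800 mg decides response, with nothing said about the starting threshold. At entry it is conditional on the baseline challenge reaching 800 mg. A reader might infer from the open-ended top stratum above 200 mg that such children are enrolled, but that stratum says nothing about 800 mg, and the protocol may cap the challenge.

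The number affected is unknown. It may be zero. It is about 3 to 11 of 35 only under the log-normal assumption with 30% above 1400 mg. Each child affected adds 1/35 = 2.9 percentage points of response that is not a change, provided tolerance is kept.

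It would go too far to say that the response rate does include unchanged children, or that the main result is in doubt. This is one secondary endpoint and its predictor table. The primary endpoint and the sample size are untouched.

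**What to change.** Amend sections 4.3 and 9.2 and Table 2.8 as follows:

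1. Keep the response rate in all treated children as it stands.
2. Report, by group, how many children already had a NOAEL of at least 800 mg at the start of their own immunotherapy: the baseline challenge for the intervention group, the week-24 challenge for the waiting list.
3. Repeat the response rate, its Fisher test and Table 2.8 in children starting below 800 mg, and base any statement that treatment produced response on that analysis.
4. In Table 2.8, replace the baseline NOAEL with the NOAEL at the start of each child's immunotherapy (week 24 for the waiting list).

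The cost is SAP wording and a few extra table rows, since the challenges are already scheduled. The restricted analysis has a slightly smaller denominator and may show a less favourable rate. It selects the waiting list on a week-24 value, so it is not a randomised comparison; but phase 2 entrants are already selected at week 24, so the existing comparison is not one either. If no child started at 800 mg or more, the two analyses coincide and one sentence can say so. Nothing here bears on who should receive immunotherapy.

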## 5 Study Methods

### 5.1 General Study Design and Plan

Single centre, randomized controlled trial of a novel active intervention (peanut oral immunotherapy) versus the status quo (peanut avoidance) in patients with peanut allergy. Two phase (package) design.

- Phase 1: Subjects randomly allocated (using minimisation methods – 80% chance of being assigned to imbalance minimising arm) to active intervention arm or waiting list arm. After 6 months all patients will be assessed for peanut allergy.
- Phase 2: Participants in waiting list arm still allergic to peanut at the end of phase 1 will be given the active intervention.

The figure below shows the study design.

## 5.2 Inclusion–Exclusion Criteria and General Study Population

### 5.2.1 Inclusion Criteria

1. Subjects aged between 7 and 15 years of age
2. Subjects with peanut allergy confirmed by a clinical history of a typical rapid onset immediate type hypersensitivity reaction to definite peanut ingestion.
3. Positive skin prick test to peanut (extract ALK–Abello, Hørsholm, Denmark) defined by wheal  $\geq 3$ mm in the presence of a negative control and positive histamine control.
4. Positive double blind placebo controlled food challenge performed according to international consensus guidelines
5. Informed consent obtained from parent / guardian or participant, as appropriate.

### 5.2.2 Exclusion Criteria

1. Clinically significant chronic illness, except for eczema, rhinitis or asthma.
2. Suspected or diagnosed allergy to peanut protein in care provider or current household member.
3. Unwillingness or inability to comply with study requirements and procedures.

## 5.3 Randomisation and Blinding

Subjects were allocated using minimisation to avoid imbalance of confounding factors between groups, with a random element using a weighting probability of 0.8 – i.e. patients were allocated to the group which would provide optimal balance with 80% probability.

The minimising variables were age (7–<12, 12–15), sex, allergy severity (mild, moderate, severe, never eaten), asthma, serum peanut IgE ( $\leq 28$ ku/l,  $>28$ ku/l), challenge threshold ( $>5$ mg, 50–200mg,  $>200$ mg) and other current food allergies.

Patients are not blinded to their randomised groups. However the primary outcome will be assessed using a double blind placebo controlled food challenge (DBPCFC). On the challenge neither the investigator, nurse nor the participant will know whether the participants dose is peanut or placebo.

### 5.4 Study Variables

The visit schedule is shown below:

Week	0	Phase 1										Phase 2									
		2	4	6	8	10	12	14	16	18	24	26*	28*	30*	32*	34*	36*	38*	40*	42*	48*
Active immunotherapy visit	1	2	3	4	5	6	7	8	9	10	11	-	-	-	-	-	-	-	-	-	-
Waiting list visit*	(Baseline)	-	-	-	-	-	-	-	-	-	2	3*	4*	5*	6*	7*	8*	9*	10*	11*	12*
Demographics	x																				
Other allergies	x																				
WAO score (historical)	x																				
DBPCFC (NOAEL, LOAEL, WAO score)	x									x											x
Peanut SPT	x									x											x
Other nut SPT	x									x											x
Peanut specific IgE	x									x											x
Total IgE	x									x											x
Basophil histamine release	x									x											x
Tryptase	x																				
QoL questionnaire	x									x											x
OIT updose*		x	x	x	x	x	x	x	x	x	x	x	x	x	x	x	x	x	x	x	x

*\*Only waiting list patients who are not desensitised to peanut after 24 weeks undergo immunotherapy from week 26 to 48*

### 5.4.1 Important Variable Definitions

- Peanut threshold (mg) – The no observed adverse effect level (NOAEL) – the highest cumulative dose of peanut that does not cause a reaction in a DBPCFC
- The lowest observed adverse effect level (LOAEL) is the lowest cumulative dose that causes a reaction (mg) in a DBPCFC
- Peanut IgE (kU/l 0 –1000) – Specific allergy antibody against peanut protein. Higher titres of IgE antibodies indicates higher probability of clinical allergy
- Basophil histamine release – Donor basophils stimulated in vitro by peanut extract at a range of concentrations. Basophil stimulation is detected by the mean fluorescent intensity of a cell surface marker (CD63). Area under the curve (AUC) of mean fluorescent intensity of CD63 (arbitrary units) and of the %CD63 positive cells against dose of peanut protein in milligrams.
- Tryptase (ng/ml) – a marker of background mast cell activation
- SPT diameter (mm 0–20) – A small amount of purified peanut is pricked on to the skin, and the diameter of the resulting wheal is recorded.

## 6 Sample Size

Based on Fisher's exact test with 90% power and 5% significance (two-sided) a sample size of 49 in each group is sufficient to detect proportions of participants with desensitisation to peanut of 64% and 30% in the intervention and control group respectively. Allowing for 5% drop out increases the sample size to 52 participants in each group and 104 subjects overall.

Based on the above we would expect 35 waiting list group patients to proceed to the active intervention in phase 2. To confirm efficacy of immunotherapy the success rate of all participants (intervention and phase 2 waiting list) should be within 10% of the success rate seen in intervention participants alone in phase 1.

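### The Section 6 rule for confirming efficacy in Package 2 compares a pooled rate with a part of itself, so a 10-point tolerance lets the treated waiting-list group fall up to 24 observed points short

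*SAP*

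**What the plan says.** The SAP describes the purpose of Package 2 in three ways.

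- **Section 3 (Introduction):** Package 2 is to confirm efficacy in the waiting-list group once treated, and to "allow an estimate of the overall success rate to within 10" per cent. This reads as a precision target.
- **Section 6 (Sample Size):** after stating that "we would expect 35 waiting list group patients to proceed to the active intervention in phase 2", the SAP says that to confirm efficacy "the success rate of all participants (intervention and phase 2 waiting list) should be within 10% of the success rate seen in intervention participants", where the reference is the phase 1 result of the intervention arm by itself. This reads as an agreement rule. It does not say whether 10% is absolute or relative, and it carries no confidence interval or error rate.
- **Section 9.2 (Secondary Efficacy Analyses):** the phase 2 incidence in the waiting-list group is reported and "compared with the incidence of desensitisation to peanut in the intervention group (end of phase 1) using Fishers exact test". No margin is given, and the Section 6 rule is not mentioned.

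**The concern.** The rule in Section 6 is the only numerical criterion for Package 2, and its two sides are not separate groups. Everyone in the reference group is also in the pool, so part of the agreement is built in. A poor result in the treated waiting-list group is diluted by the intervention results before it is judged. The 10% therefore appears stricter than it is, and confirmation could be declared when the second group did clearly worse than the first. The SAP also does not say which of Sections 3, 6 and 9.2 governs if they point different ways.

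**Working it through.** **Inputs (all from SAP Section 6).**
- Test, power and size: "Based on Fisher's exact test with 90% power and 5% significance (two-sided) a sample size of 49 in each group is sufficient".
- Assumed rates: 64% with intervention and 30% with control.
- Dropout allowance: "Allowing for 5% drop out increases the sample size to 52 participants in each group and 104 subjects overall".
- Expected number treated in phase 2: 35.
- Tolerance: 10%.

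**The plan's own figures reproduce.**
- The two-proportion formula with continuity correction gives 49 per group for 64% v 30%. Exact Fisher power by enumeration is 90.6% at 49 per group (89.6% at 48).
- Dropout: 49/0.95 = 51.6, so 52.
- Entering phase 2: 0.70 × 49 = 34.3 and 0.70 × 52 = 36.4, so 35 is reasonable.

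**Dilution.** Let p1 be the intervention rate (n1 participants) and p2 the treated waiting-list rate (n2 participants). Then

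pooled − p1 = (n1·p1 + n2·p2)/(n1 + n2) − p1 = [n2/(n1 + n2)] × (p2 − p1).

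With n1 = 49 and n2 = 35 the factor is 35/84 = 0.417.

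**Largest observed shortfall that still passes.**
- 10% absolute: 0.10/0.4167 = 24.0 points, i.e. 64% v 40%, pooled 54.0%. With n1 = 52 it is 24.9 points.
- 10% relative (6.4 points at 64%): 0.064/0.4167 = 15.4 points. With n1 = 52 it is 15.9 points.

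**Chance that the rule is met.** Exact binomial enumeration, n1 = 49, n2 = 35, true p1 = 64%, counting a pooled rate no more than the tolerance below p1:

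| True phase 2 rate | 10% absolute | 10% relative |
|---|---|---|
| 64% | 0.99 | 0.95 |
| 50% | 0.82 | 0.56 |
| 40% | 0.49 | 0.19 |
| 35% | 0.31 | 0.08 |
| 30% | 0.16 | 0.03 |

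Applying the absolute limit in both directions gives 0.98 in the first row and leaves the others unchanged to two decimals.

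**Against the Section 9.2 test.** Take 31/49 (63.3%) and 14/35 (40.0%). The pooled rate is 45/84 = 53.6%, which is 9.7 points below 63.3%, so the rule is met. Fisher's test on the same counts gives p = 0.046, with the waiting-list group worse. The exact 95% CI for 14/35 is 23.9% to 57.9%. This example sits on the boundary:
- With 31/49 held fixed, 13/35 fails the rule (10.9 points) and 15/35 is not significant (p = 0.078).
- At true rates of 64% and 40%, the probability that the rule is met while Fisher's test is significant is about 0.06.

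**Against Section 3.** The 95% half-width for a pooled rate of 64% is 1.96 × √(0.64 × 0.36/84) = 10.3 points. The 10% in Section 3 is therefore about what 84 treated participants deliver as precision.

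**The case against.** The strongest defence is that no operative analysis depends on this sentence. It stands in the sample size section and does not recur in the endpoints, efficacy analyses or table list. Section 9.2 already plans the direct comparison, and Section 9 requires an effect size and 95% CI with each test. The sentence may also be the Section 3 precision target reworded by mistake, since the half-width matches. Most of this stands, and it limits the weight of the point. It does not remove the point, because Section 6 still presents the rule as what confirms efficacy. Nor can the Fisher test take its place: its power for 64% v 40% at 49 and 35 is only about 57%, and a non-significant result would not show similarity. That the rule began as a precision target is an inference; the sections need aligning either way.

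A reader might infer more than the SAP supports:
- **That the rule always passes a group that is 24 points worse.** The 24 points is the break-even for observed rates. At a true 24-point deficit the rule passes about half the time, and larger deficits are mostly rejected.
- **That Sections 6 and 9.2 will regularly contradict each other.** They can, but only near the boundary, with probability about 6% at a true 40%.
- **That the treated waiting list should be benchmarked against 30% as its own untreated rate.** Sections 5.1 and 5.4 admit to phase 2 only waiting-list participants who are still allergic, so their phase 1 conversion is zero by selection. The 30% belongs to the whole waiting-list arm.

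**Conclusion.** The point holds as a flaw in the Section 6 rule. Comparing the pool with its own larger part shrinks the difference between the groups to 0.417 of its size, so the stated tolerance of 10 points is in effect 24 points on the comparison of interest, or about 15 if 10% is relative. These figures assume 49 intervention and 35 treated waiting-list participants and an intervention rate of 64%; the dilution itself does not depend on those values being exact. The same 10% also has two meanings in Sections 3 and 6, neither of them tied to the Section 9.2 test.

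A reader might conclude that the trial's efficacy finding is unsafe. The SAP does not support that: phase 2 desensitisation is a secondary endpoint (Section 4.2.2), and the randomised primary comparison in Section 9.1 does not use this rule. The point should be fixed, but it is not critical.

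**What to change.** - **Section 6:** delete the pooled-versus-part rule.
- **Section 9.2:** base the Package 2 conclusion on the treated waiting-list participants' own success rate with an exact 95% CI, and on the direct difference (treated waiting list minus intervention) with its 95% CI. Sections 9 and 9.2 already provide most of this.
- **Sections 3 and 6:** keep the pooled rate only as a precision statement, about ±10.3 points at 64% with n = 84, and make the wording agree with Section 9.2.
- **Any numerical benchmark for confirmation:** the sponsor should justify it in advance, state it as absolute or relative, and take account of the selection into phase 2. The 30% for the whole waiting-list arm should not be used as that subgroup's untreated rate.

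**Cost:** SAP wording only, with no new data. The drawback is that the direct difference is imprecise: at 64% in both groups its half-width is 1.96 × √[0.64 × 0.36 × (1/49 + 1/35)], about ±21 points. Package 2 can then support only a cautious statement about consistency between the groups.
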